	8.2.2 Study Drug Accountability	
	8.2.2 Study Drug Accountability8.2.3 Randomization and Blinding	19
	8.2.2 Study Drug Accountability	19
	8.2.2 Study Drug Accountability8.2.3 Randomization and Blinding	19
	 8.2.2 Study Drug Accountability 8.2.3 Randomization and Blinding 8.2.4 Study Medication	19
	8.2.2 Study Drug Accountability8.2.3 Randomization and Blinding	19 19

10. ASSESSME	NT OF SAFETY	
10.1 ADV	erse Events	
10.1.1	Reporting Adverse Experiences	
10.1.2	Definitions	

[figure not shown]
10	0.1.3 Serious Adverse Events (SAEs)	
11. CON	COMITANT MEDICATIONS	
11.1	PROHIBITED MEDICATIONS	
11.2	OTHER MEDICATIONS TAKEN DURING THE STUDY	
12. STAT	ISTICAL METHODS	
12.1	DETERMINATION OF SAMPLE SIZE	
12.2	STATISTICAL AND ANALYTICAL PLAN	
12.3	GENERAL STATISTICAL ISSUES	34
12.5		
12.0	CS	
12.0		
13. ETHI	CS Subject Information and Consent Institutional Review Board	
13. ETHI 13.1	CS Subject Information and Consent Institutional Review Board Monitoring Case Report Forms	
13. ETHI 13.1 13.2	CS Subject Information and Consent Institutional Review Board Monitoring Case Report Forms Study Record Retention	
13. ETHI 13.1 13.2 13.3 13.4 13.5	CS SUBJECT INFORMATION AND CONSENT INSTITUTIONAL REVIEW BOARD MONITORING CASE REPORT FORMS STUDY RECORD RETENTION DATA QUALITY ASSURANCE	
13. ETHI 13.1 13.2 13.3 13.4	CS Subject Information and Consent Institutional Review Board Monitoring Case Report Forms Study Record Retention	

3. **PROTOCOL SYNOPSIS**

Test Drugs:	Proellex [®] (Telapristone Acetate): 12 mg gelatin capsules
Protocol Number:	ZPU-203EXT
Study Purpose:	To determine the safety of extended treatment with Proellex in women who have successfully completed either study ZPV-201 or ZPU-203 and meet eligibility criteria.
Study Design and Duration Of Treatment:	This study is an open-label, multi-center extension study to evaluate the safety of continued treatment with Proellex in subjects who successfully completed either study ZPV-201 or ZPU-203. The study requires 16 visits and is approximately 13 months in duration (up to 15 months for selected sites). Subjects will be treated orally with 12 mg Proellex/day for three 18-week courses, each separated by an ODI. Throughout the study women will record study information in the diary, PBAC, and questionnaires as outlined in the study procedures.
	The start of the first 18-week course of treatment (Course 1) should commence no later than 4 days after the end of bleeding, i.e. at visit 24 (or Visit 19, see Study Procedures below) of the previous study. Once dosing for Course 1 is stopped, subjects will be followed until menses returns. The start of the second and third 18 week courses of treatment (Courses 2 and 3) will commence no later than 4 days after the end of bleeding in the subject's menses following withdrawal of drug after the previous course has been completed.
	At selected sites subjects will commence dosing on the first day of bleeding in their next menstrual cycle after Visit 19 or Visit 24 (about 3 weeks after V19 or 24). The start of the second and third courses of treatment will start on the first day of bleeding in the subject's second menses following withdrawal of study drug.
	During the ODI, subjects will continue to record study information in the daily paper diary and PBAC charts.
	Any subject who has any 28-day period during treatment (not including the ODIs) without a bleeding score >1 will be deemed to have achieved amenorrhea. Subjects who do not achieve amenorrhea after 8 weeks of treatment will exit the study. After completion of 3 courses of treatment, subjects will be followed through the subsequent menstrual event (recovery menses).
	A DSMB will review any liver safety events (LFTs $\geq 3 \times ULN$ or bilirubin $\geq 2 \times ULN$).
Subject Population:	The study will enroll women who have successfully completed either study ZPV-201 or ZPU-203 and meet eligibility criteria.
Number of Subjects:	Up to about 60 subjects
Number of Sites	Approximately 10 sites
Study Duration:	Total participation in the study is approximately 13 months.

:	
Study Endpoints	Endpoints will be:
	• Percentage of subjects who become amenorrheic
	• Change in UFS-QOL Symptom Severity score comparing to the previous study baseline and study baseline
	• Change in the individual UFS-QOL sub scores
	Change in PBAC scores
	• Percentage change from parent study baseline and study baseline in total uterine fibroid volume measured by MRI
	• Incidence of significant adverse events
	Changes in physical examination results
	Changes in clinical laboratory results
	Changes in liver function to values
	• Unexpected or excessive vaginal bleeding
	Endometrial thickness assessed using vaginal ultrasounds
	• Change in number and intensity of bleeding days over the course of the treatment and ODI periods
	• Pathology of the endometrium assessed by biopsies.

Statistical Methods:	Summaries for quantitative variables include the sample size, mean, median, standard deviation, minimum, and maximum. Summaries for categorical variables include the number and percent of patients for each outcome.
	Continuous efficacy endpoints, such as the change from baseline in uterine tumor volumes will assess treatment effect using a within- group t-test or appropriate non-parametric technique. The percentage of subjects becoming amenorrheic will be determined.

[figure not shown]
5. LIST OF ABBREVIATIONS

AE	Adverse event
CRF	Case report form
DHEA	Dehydroepiandrosterone
dL	Deciliter
FSH	Follicle-stimulating hormone
GCP	Good Clinical Practice
GnRH	Gonadotrophin releasing hormone
g	Grams
ICH	International Conference on Harmonization
IRB	Institutional Review Board
IND	Investigational new drug
IUD	Intra-uterine device
kg	Kilogram(s)
LD_{50}	Median lethal dose
LH	Luteinizing hormone
m	Meters
MBL	Menstrual Blood Loss
mg	Milligram(s)
mL	Milliliter
ng	Nanograms
OC	Oral Contraceptive
ODI	Off-Drug Interval
PBAC	Pictorial Blood Loss Assessment Chart
PCOS	Polycystic Ovarian Syndrome
РК	Pharmacokinetic
RBC	Red blood cell
SAE	Serious adverse event
UFSQOL	Uterine Fibroid Symptom Quality of Life Survey
UFS-QOL	Uterine Fibroid Symptom Quality of Life Survey
WBC	White blood cell

6. BACKGROUND INFORMATION

[figure not shown]
6.1 Rationale for Current Study

Repros believes telapristone offers the potential to provide significant symptomatic relief to women that suffer from a variety of reproductive disorders in which progesterone may be implicated.

[figure not shown]
Based on findings from the recently completed ZP-204 low dose study of oral Proellex, doses from 1 mg up to 12 mg daily were administered for 10 consecutive weeks with no observed elevations of liver enzymes or even trends towards increasing liver enzymes with increasing dose. At the same time induction of amenorrhea was seen in a consistent fashion starting at a 3 mg daily dose as long as trough levels of the drug were observed. The

sponsor believes there is a direct correlation of symptomatic relief for uterine fibroids and endometriosis with induction of amenorrhea.

dosed for 4 months (120 days) after which time the drug is withdrawn to allow for menses to return. Once menses has occurred women may resume treatment for another dosing period. In this fashion the drug can be used to control the symptoms of endometriosis and fibroids until the onset of menopause.

6.2 Non-Clinical Data

[figure not shown]

6.3 Clinical Data/Human Experience

In addition to the preclinical studies, a Phase I/II study of orally administered Proellex in pre-menopausal women with symptomatic leiomyomata had been completed. The objectives of this study were to test the safety, efficacy, and pharmacokinetics of three doses of Proellex (12.5 mg, 25 mg, and 50 mg) administered as a once daily dose for 90 days, with study visits at one-month intervals. The safety and effectiveness of Proellex was compared to placebo and the active control leuprolide acetate for depot suspension (Lupron Depot). At the conclusion of this study, exploratory analyses showed statistically significant efficacy differences between treatment groups (overall and pairwise).

6.5 Ethical Conduct of the Study

This trial will be conducted in strict compliance with the protocol and all applicable FDA regulations and GCP guidelines to insure Good Clinical Practice standards. IntegReview, [name], will serve as an Institutional Review Board (IRB) for clinical sites who will accept their review.

6.6 Drug Safety Monitoring Board (DSMB)

A DSMB will review the data from any subject who has elevation of LFTs \geq 3 x ULN and/or a bilirubin level \geq 2 x ULN.

7. TRIAL OBJECTIVES AND PURPOSE

[figure not shown]
The primary objective of this study is to determine the safety of orally administered Proellex administered at 12 mg/day for up to 3 courses of treatment (18 weeks each), each separated by an Off-Drug Interval (ODI), to women who have completed either ZPV-201 or ZPU-203.

To further investigate the effect of the timing of start of dosing upon the onset of amenorrhea, at selected sites the start of dosing in each cycle will be on the first day of bleeding rather than 0-4 days after stopping bleeding.

8. TRIAL DESIGN

8.1 Study Endpoints

- Percentage of subjects who become amenorrheic over the course of the study
- Change in UFS-QOL Symptom Severity Score comparing to the previous study baseline and study baseline
- Change in the individual UFS-QOL subscores over the course of the study
- Change in PBAC scores over the course of the study
- Percentage change from parent study baseline and study baseline in total uterine fibroid volume measured by MRI

8.2 Study Design

8.2.1 Overview of Study Design

This study is an open-label, multi-center extension study to evaluate the safety of continued treatment with Proellex in subjects who successfully completed either study ZPV-201 or ZPU-203. The study requires 16 visits and is approximately 13 months in duration. Subjects will be treated orally with 12 mg Proellex/day for three 18week courses, each separated by an ODI. Subjects will use only sanitary supplies provided by the sponsor. Throughout the study women will record study information in the diaries and questionnaires as outlined in the study procedures.

Any subject who has **any** 28-day period during treatment (not including the ODIs) without a bleeding score >1 will be deemed to have achieved amenorrhea (in both the current or the previous study). Visit 1 of this study will also be Visit 24 of the previous study unless

the subject failed to achieve amenorrhea in the previous study. Such subjects may enroll at Visit 19 (after first recovery menses) in the previous study. Subjects who do not achieve amenorrhea after 8 weeks of treatment in this study will exit the study.

The start of the first 18-week course of treatment (Course 1) should commence no later than 4 days after the end of bleeding in the last menses, which should coincide with Visit 19 or 24 of the previous study. Once dosing for Course 1 is stopped, subjects will be followed until menses returns. The start of the second and third 18 week courses of treatment (Courses 2 and 3) will commence no later than 4 days after the end of bleeding following withdrawal of drug after the previous course has been completed.

At *selected sites* subjects will commence dosing on the first day of bleeding in their next menstrual cycle after Visit 19 or Visit 24 (about 3 weeks after V19 or 24). The start of the second and third courses of treatment will start on the first day of bleeding in the subject's *second* menses following withdrawal of drug.

During the ODI, subjects will continue to record study information in the daily paper diary.

After completion of 3 courses of treatment, subjects will be followed through the subsequent menstrual event (recovery menses).

A DSMB will review any liver safety events (LFTs $\geq 3 \times ULN$ or bilirubin $\geq 2 \times ULN$).

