12.2.3 Percentage Change in PBAC Scores

The percentage change in PBAC scores over each 28 day period of the course will be recorded and compared to baseline to determine onset of benefit. Additionally PBAC scores will be used to monitor the level of vaginal bleeding during the ODI.

Within treatment group paired t-tests will evaluate treatment effect. While the primary assessment will be after each 18 week treatment course, summaries will be prepared for each of the other visits. If data are missing, a last observation carried forward procedure will be used, including the baseline, if necessary. Non-parametric methods will be employed as appropriate.

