12.3 General Statistical Issues

A Statistical Analysis Plan (SAP) will be finalized prior to unblinding the study. For the efficacy variables a last observation forward approach will be used to impute missing data to generate a complete ITT data. If there are no post-baseline efficacy data then a value of no change will be imputed for the

missing efficacy measure. Statistical significance will be declared if the twosided p-value is ≤ 0.05 .

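### As written, LOCF in Section 12.2.3 can fill a missing off-drug PBAC score with the last on-drug score, and Section 8.2.1 leaves PBAC out of off-drug recording

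*Combined protocol and SAP*

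**What the plan says.** **Analysis.** Section 12.2.3 compares PBAC with baseline over successive 28-day periods of each course. It then gives PBAC a second use: "Additionally PBAC scores will be used to monitor the level of vaginal bleeding during the ODI". On timing it says: "While the primary assessment will be after each 18 week treatment course, summaries will be prepared for each of the other visits". On missing data it says: "If data are missing, a last observation carried forward procedure will be used, including the baseline, if necessary". Section 12.3 repeats the rule in general terms: "For the efficacy variables a last observation forward approach will be used to impute missing data to generate a complete ITT data". Neither section separates on-treatment from off-drug windows.

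**Recording.** The synopsis (Study Design and Duration of Treatment) asks for two instruments in the ODI: "During the ODI, subjects will continue to record study information in the daily paper diary and PBAC charts". The parallel sentence in Section 8.2.1 stops earlier: "During the ODI, subjects will continue to record study information in the daily paper diary". The general recording sentences differ in the same way. The synopsis has "Throughout the study women will record study information in the diary, PBAC, and questionnaires as outlined in the study procedures", and Section 8.2.1 has "Throughout the study women will record study information in the diaries and questionnaires as outlined in the study procedures".

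**Course structure.** Subjects receive up to three 18-week courses separated by ODIs and are followed through a recovery menses after the third. Under the synopsis and Section 8.2.1, a subject who has not achieved amenorrhea after 8 weeks of treatment leaves the study.

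**The concern.** LOCF assumes that the last recorded value is a fair stand-in for the missing one. That assumption fails when drug is withdrawn. Section 6.1 explains that the drug is stopped so that menses can return, so the off-drug score is meant to reflect a different state from the on-drug score before it. Carrying the on-drug score forward replaces the very bleeding that Section 12.2.3 sets out to monitor, and does so in the reassuring direction.

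Two features make this worth correcting. The primary objective is safety, and the study is open-label with a single regimen and no control group, so no comparison arm would show that return bleeding had been understated. An imputed summary also appears complete, so its sample size would not reveal how many charts were missing. The shorter sentence in Section 8.2.1 makes missing off-drug charts more likely at any site that works from that section alone.

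**Working it through.** The plan states no figure on this point, so there is none to reproduce. The check is a comparison of texts, followed by the algebra of one carried value.

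**Step 1: is PBAC meant to be recorded off drug?**

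| Place | Instruments named |
|---|---|
| Synopsis, ODI sentence | daily paper diary and PBAC charts |
| Section 8.2.1, ODI sentence | daily paper diary |
| Synopsis, whole-study sentence | diary, PBAC, questionnaires |
| Section 8.2.1, whole-study sentence | diaries, questionnaires |
| Section 12.2.3 | PBAC used to monitor ODI bleeding |

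The synopsis and Section 12.2.3 agree. Section 8.2.1 omits PBAC but does not rule it out.

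**Step 2: does the LOCF rule reach the off-drug window?** The ODI monitoring sentence, the sentence on summaries at other visits and the LOCF sentence all stand in Section 12.2.3. The LOCF sentence applies whenever data are missing. Nothing limits it to the on-treatment percentage-change analysis. Followed as written, it can therefore fill an off-drug score; the text neither says that it will nor excludes it.

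**Step 3: which value would be carried?** For an ODI after a course with charts, it is the last on-drug score. Subjects still on treatment late in a course have passed the 8-week amenorrhea rule, so that score tends to be low. It need not be zero: amenorrhea requires only one 28-day period without a bleeding score above 1, and a subject may bleed later in the course. If no on-treatment chart existed at all, the rule falls back to baseline and this direction argument does not apply.

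**Step 4: direction.** Let B be the baseline score, L the last on-drug score and R the true off-drug score.

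- Percentage change with the carried value: 100 × (L − B)/B
- True percentage change: 100 × (R − B)/B
- Understatement: 100 × (R − L)/B percentage points

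This is positive whenever R exceeds L. If a share m of subjects is imputed in this way, the group mean is understated by m times the average of this quantity among them.

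**Step 5: size.** The documents give no value for B, L, R or m, so the size cannot be derived. To show the mechanism only, take assumed scores B = 200, L = 0 and R from 100 to 300:

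- carried: (0 − 200)/200 = −100%
- true: (100 − 200)/200 = −50% to (300 − 200)/200 = +50%
- understatement for that one subject: 50 to 150 percentage points

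The number of off-drug windows is at most 60 subjects × 3 withdrawals = 180. That ceiling requires every subject to complete all three courses. It counts windows, not missing charts.

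**The case against.** **A reader might infer that Section 8.2.1 confines off-drug recording to the diary, so that no PBAC would exist.** The text does not support this. Section 8.2.1 is silent on PBAC, and its plural reference to diaries may include the chart. It is an overview that defers to study procedures not in the supplied text, and those may schedule the charts. No passage gives it precedence over the synopsis, which does require them. The singular diary in the ODI sentence, and the synopsis's separate listing of diary and charts, still make the mismatch real.

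**A reader might infer that off-drug bleeding would go unseen or that a safety endpoint would be biased.** That also goes too far. The diary carries a bleeding intensity score, and the synopsis lists number and intensity of bleeding days in both treatment and ODI periods as a separate endpoint. Section 10.1.1 lists adverse events for up to 30 days after the last dose. No passage derives the endpoint on unexpected or excessive vaginal bleeding from PBAC, or says that it is imputed.

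**LOCF may not be intended for the ODI.** The percentage-change analysis concerns periods of the course, its primary assessment follows each course, and Section 12.3 attaches LOCF to efficacy variables. ODI monitoring is an additional use with no stated test. If no site returned off-drug charts, an empty table might be more likely than a misleading one. Section 12.3 also foresees a finalised SAP that could settle the matter.

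These arguments make the bias conditional and remove any claim about its size. They do not remove the gap: Section 12.2.3 plans summaries at other visits and states an imputation rule without an off-drug exception. A few missing charts among many returned ones is the case in which imputation would pass unnoticed.

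**Conclusion.** The point holds as a minor one. As written, Section 12.2.3 permits a missing off-drug PBAC score to be filled from the on-drug period, which would understate return bleeding. The omission in Section 8.2.1 raises the chance of missing charts but is, taken alone, only a wording mismatch with the synopsis.

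The conclusion depends on three conditions: some off-drug charts are missing, LOCF is applied to the off-drug summaries, and the last on-drug score is below the true off-drug score. The 8-week exit rule makes the third likely; the first two are open on the supplied text. The documents support the direction of the bias only. The 50 to 150 point illustration rests on assumed scores and the 180 windows are a ceiling, so neither estimates the effect.

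**What to change.** In Section 12.2.3, add that PBAC in off-drug windows (both ODIs and the recovery menses after Course 3) is summarised as observed and is never imputed from an on-treatment value, and that the number of missing charts is reported for each window. Carry the same restriction into the SAP so that the general LOCF rule in Section 12.3 does not override it.

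Reconcile the ODI recording sentence in Section 8.2.1 with the synopsis sentence, and check that the study procedures agree.

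The cost is about one sentence in each place. No new data collection is implied for the ODIs, since the synopsis already asks for the charts there. The downside is that some off-drug summaries will have fewer subjects, which the reported counts will make visible.

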8.2.2 Study Drug Accountability

The designee assigned by the Principal Investigator at each site will maintain accurate records of receipt of all study drugs, including dates of receipt. Reasons for deviation from the expected dispensing regimen must also be recorded. A Drug Dispensing Form will be provided for this purpose. To satisfy regulatory requirements regarding drug accountability and destruction, the Principal Investigator at each site will return all used, unused, empty, and partially used study medication with dispensing records to the Sponsor for final accountability and disposal, after accountability has been verified by the study monitor.

[figure not shown]
8.2.3 Randomization and Blinding

As the study is open-label there will be no randomization or blinding.

8.2.4 Study Medication

All study drugs will be supplied by Repros Therapeutics Inc. Test drug, Proellex will be supplied in 40 count bottles and will be packaged by a clinical supplies contract vendor designated by Repros Therapeutics Inc.

8.3.1 Inclusion Criteria

Subjects must meet the following criteria:

- Completed either study ZPV-201 or ZPU-203
- Agreement not to attempt to become pregnant during the trial
- Agreement to use alcohol in moderation and record the daily consumption (note: elevated liver enzymes may result in discontinuation from the study)
- Ability to complete a daily subject diary and study procedures in compliance with the protocol
- Agreement to use **only** sanitary supplies provided by the sponsor throughout the study
- Women of child-bearing potential must be willing to use doublebarrier contraception during the study and off-drug intervals. Acceptable double-barrier methods are: male condom with spermicide; male condom with diaphragm; diaphragm containing spermicide plus additional intra-vaginal spermicide
- Has a negative pregnancy test at Visit 1
- Subject is available for all treatment and follow-up visits

8.3.2 Exclusion Criteria

Subjects meeting any of the following criteria will be excluded from the study:

- Subject had a significant decrease in bone mineral density while participating in ZPV-201 or ZPU-203 (total hip or spine measurement decreased by more than 5%)
- Subject has undergone hysterectomy and/or bilateral oophorectomy since enrollment in ZPV-201 or ZPU-203.
- Subject is pregnant or lactating or is attempting or expecting to become pregnant during the entire study period
- Subjects with abnormally high liver enzymes or liver disease. (ALT or AST exceeding 2 x ULN AND total bilirubin exceeding 1.5 x ULN at Visit 1 and confirmed on repeat).
- Subject has a hemoglobin of <7.5 g/dL at Visit 1
- At sponsor discretion, subject had poor compliance in study ZPV-201 or ZPU-203
- Concurrent use of any testosterone, progestin, androgen, estrogen, anabolic steroids, DHEA or hormonal products for at least 2 weeks prior to Visit 1

- Use of oral contraceptives in the 30 days preceding screening. Use of Depo-Provera[®] in the preceding 10 months.
- Use of GnRHas (e.g. Lupron Depot) within 3 months prior to screening (Lupron Depot must have a wash-out period of 3 months prior to screening)
- Has an IUD in place
- Current cervical dysplasia classified as Atypical Squamous Cells of Undetermined Significance (ASCUS) associated with high-risk human papilloma virus (HPV)
- Current diagnosis of Low/High Grade Squamous Intraepithelial Lesion (LGSIL or HGSIL), endometrial polyps or hyperplasia
- Observation or history of abnormal endometrial biopsy including the presence of EIN
- Recent history (within past 6 months) of alcoholism or drug abuse
- Endometrial stripe ≥18 mm in thickness at Visit 1 (subject may be enrolled with sponsor approval)
- Subject is currently taking cimetidine or spironolactone or has taken them in the last 30 days
- Clinically significant abnormal findings on Visit 1 examination and laboratory assessments or any condition which in the opinion of the investigator would interfere with the participant's ability to comply with the study instructions or endanger the participant if she took part in the study.

Page 24 of 50

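### The numeric liver exclusion needs both ALT/AST and bilirubin raised, so by itself it does not exclude a woman with one marker at the DSMB-review level

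*Combined protocol and SAP*

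**What the plan says.** All references are to the combined protocol and SAP.

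- **Entry rule (8.3.2).** The liver criterion opens with "Subjects with abnormally high liver enzymes or liver disease" and continues in parentheses: "ALT or AST exceeding 2 x ULN AND total bilirubin exceeding 1.5 x ULN at Visit 1 and confirmed on repeat". The connector is underlined in the source.
- **Other entry wording.** The last bullet of 8.3.2 excludes for "Clinically significant abnormal findings on Visit 1 examination and laboratory assessments or any condition which in the opinion of the investigator would interfere" with participation or endanger the woman. The alcohol item in 8.3.1 adds that "elevated liver enzymes may result in discontinuation from the study".
- **DSMB trigger.** Section 6.6 says "A DSMB will review the data from any subject who has elevation of LFTs" of at least 3 x ULN and/or bilirubin of at least 2 x ULN. Section 8.2.1 says "A DSMB will review any liver safety events" and joins the same two limits with *or*, as does the synopsis. Either marker is enough.
- **SAE rule (10.1.2, 10.1.3).** Transaminases that rise above 3 x ULN are reportable as SAEs, with no bilirubin condition.
- **Timing (8.2.1).** "Visit 1 of this study will also be Visit 24 of the previous study", unless the woman failed to reach amenorrhea there, in which case she may enter at Visit 19.

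**The concern.** The entry rule needs two raised markers, while the on-study alarm needs one. A specific numeric rule with its connector underlined can lead a site to accept an isolated elevation, even one at the level that the protocol sends to its DSMB.

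Safety is the primary objective (section 7), and liver has its own DSMB trigger and its own SAE rule. Entry normally follows parent-study treatment, so a raised Visit 1 marker may reflect earlier exposure. For bone, the same exclusion list bars women who lost more than 5% of density in the parent study; for liver it sets no single-marker limit.

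On the numeric rule alone, such a woman could start up to 3 x 18 = 54 weeks of dosing. In an open-label study without a comparator, her later liver values would be hard to attribute. It would also be unclear how an SAE rule worded around an increase above 3 x ULN applies to someone who entered above it.

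**Working it through.** There is no stated figure to reproduce. The check compares two rules.

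**Inputs.** Let A be the higher of ALT and AST and B total bilirubin, both in multiples of ULN and confirmed on repeat.

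- Current exclusion (8.3.2): E = (A > 2) and (B > 1.5).
- DSMB level (6.6, 8.2.1): D = (A ≥ 3) or (B ≥ 2). This assumes that LFTs include ALT and AST; the visible text does not define the term.

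**Where D holds but E does not.** Not-E means A ≤ 2 or B ≤ 1.5. Crossing this with D gives four combinations. Two are impossible (A ≤ 2 with A ≥ 3; B ≤ 1.5 with B ≥ 2). Two remain:

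- (a) A ≥ 3 and B ≤ 1.5
- (b) B ≥ 2 and A ≤ 2

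They do not overlap, and neither has an upper limit.

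**Effect of a single-marker clause.** Let P = E or (A ≥ 3) or (B ≥ 2), before any waiver.

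| A | B | DSMB level | Excluded now (E) | Excluded with clause (P) |
|---|---|---|---|---|
| 5 | 1 | yes | no | yes |
| 10 | 1.5 | yes | no | yes |
| 1 | 2.5 | yes | no | yes |
| 3 | 1.6 | yes | yes | yes |
| 2.1 | 1.6 | no | yes | yes |
| 2.1 | 1 | no | no | no |

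**Grid check of the logic.** A and B each run from 0 to 10 in steps of 0.05, giving 201 x 201 = 40,401 cells.

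- Below both triggers: 60 x 40 = 2,400. At DSMB level: 40,401 - 2,400 = 38,001.
- Region (a): 141 x 31 = 4,371. Region (b): 161 x 41 = 6,601. Together 10,972 DSMB-level cells are not excluded now.
- With P, no DSMB-level cell is left unexcluded and no cell below both triggers is newly excluded. Both zeros follow by construction, because P uses the DSMB limits.
- Replacing *and* with *or* at the existing cut-offs (A > 2 or B > 1.5) would newly exclude 19 x 31 + 9 x 41 = 589 + 369 = 958 cells below both triggers.

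These counts test the logic only. Cells are not women, and the documents give no distribution of Visit 1 values.

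**The case against.** The strongest reply is that 8.3.2 excludes on any one criterion, and the last bullet covers clinically significant laboratory findings at Visit 1. An investigator would have to judge a confirmed value at DSMB level not clinically significant before such a woman could be dosed. The lead-in also ends with its own full stop before the parenthesis. Read as free-standing, it excludes ALT 5 x ULN outright.

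Further points are fair:

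- Entrants must have completed a parent study, whose liver-stopping rules are not visible and may already have removed such women.
- Visit 1 normally falls after the recovery menses, so the typical entrant is off drug, and an elevation would have to persist and be confirmed on repeat.
- Section 6.1 reports no enzyme elevations at 1 to 12 mg over 10 weeks, although that is shorter than one 18-week course.
- Section 9 and the study procedures to which the synopsis points are not in the text supplied and may hold further liver checks.
- The underlined connector suggests a deliberate choice, and an entry limit need not equal a DSMB-review trigger.

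All of this lowers the likely consequence. It does not supply a single-marker limit. The lead-in and the last bullet work by judgement at about 10 sites, the 8.3.1 note is permissive and has no number, and 6.6 prescribes review rather than a bar to entry.

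A reader might infer that the protocol knowingly admits women with marked liver elevations, or that it has no other protection against this. The documents do not support either reading: the other wording can exclude or stop such a woman, an enrolled woman at that level would go to DSMB review, and unseen sections cannot be counted as missing.

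**Conclusion.** The point holds for the numeric rule taken by itself: it leaves regions (a) and (b) open, and both lie at the protocol's own DSMB-review level. Whether any woman would enter through the gap depends on site judgement and on text not seen. The number affected cannot be estimated and is probably small.

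The conclusion rests on two assumptions: LFTs include ALT and AST, and the visible text of 8.3.2 contains the whole numeric rule. If LFTs cover other tests, the comparison speaks only to ALT, AST and bilirubin.

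This is a cheap improvement to a safety criterion. It does not show that the study is unsafe or that its results would be invalid.

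**What to change.** Keep the current criterion and add to it: *or ALT or AST ≥3 x ULN regardless of bilirubin, or total bilirubin ≥2 x ULN regardless of ALT/AST, at Visit 1 and confirmed on repeat*. The phrase *regardless of* matters. A limit on one marker *alone* could be read as requiring the other to be normal, which would leave out, for example, ALT 5 x ULN with bilirubin 1.3 x ULN.

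Allow documented sponsor approval only for benign isolated hyperbilirubinaemia with ALT/AST ≤2 x ULN. The list already uses this route for endometrial stripe: "subject may be enrolled with sponsor approval". The waiver can apply only within region (b). Apart from it, no woman at the ALT/AST or bilirubin DSMB level would pass the numeric rule. It would be wrong to say that none at that level could enter, because waived women still could.

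Lowering the single-marker limits to 2 x and 1.5 x ULN is optional and debatable, because it would also exclude women below both DSMB triggers, such as ALT 2.1 x ULN with normal bilirubin.

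The cost is one clause, one approval route to document, and possibly a few fewer eligible women.
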